Mechanisms of belatacept effect on alloimmunity and antiviral response after kidney transplantation

An Investigator-Initiated Research Proposal Concept # 56950 BMS study # IM 103-309

[name]. Principal Investigator UCLA Division of Kidney Transplantation [name] [contact]

[name]. Co-investigator Director of the UCLA Immunogenetics Center Department of Pathology and Laboratory Medicine [name]

[name]., Ph.D. Co-investigator UCLA Division of Infectious Diseases [name]

SYNOPSIS

Title of Study: Mechanisms of belatacept effect on alloimmunity and antiviral response after kidney transplantation

Estimated Number of Study Centers and Countries/Regions: 1

Study Phase: 4

Research Hypothesis: Switching to a belatacept-based immunosuppression regimen after kidney transplant will have a significant impact on antibody and T cell-mediated immune response as compared with control patients as measured in peripheral blood at 6 months after belatacept switch and comparable safety and efficacy as compared with calcineurin inhibitor (CNI) based regimens.

Primary Objective: To analyze the effect of switching from CNI to belatacept in patients with evidence of CNI toxicity on the development and maintenance of immune memory in response to both alloantigen and viral antigens commonly encountered after transplant, and to assess the safety and efficacy of conversion to belatacept as maintenance immunosuppression in combination with prednisone and mycophenolate mofetil.

Study Design: Open label, single center clinical trial. Patients with evidence of CNI toxicity will be eligible for switch to belatacept-based regimen within the first three months after transplant. All enrolled subjects will also receive concomitant maintenance immunosuppression with mycophenolate mofetil and corticosteroids.

Duration of Study: 6 months, with option to extend to 12 months of belatacept treatment Number of Subjects: 20 Study Population: Kidney transplant recipients within the first three months of their first transplant with evidence of CNI toxicity.

Test Product, Dose and Mode of Administration, Duration of Treatment: Study patients will receive intravenous belatacept at 5mg/kg every two weeks at day 1 and weeks 2, 4, 6, and 8, and then monthly at months 3, 4, and 5. At month 6 patients may elect to continue for an additional six month period of belatacept administration. Peripheral blood mononuclear cells (PBMCs) and sera for antibody testing will be collected at time of study entry and at 4, 8, 12, and 24 weeks after belatacept start, frozen and banked at our center, and analyzed in batch fashion for development of humoral and cell mediated immunity. Patients who elect to receive an additional 6 months of belatacept treatment will undergo additional immunologic analysis at 1 year after study entry.

Reference Therapy, Dose and Mode of Administration, Duration of Treatment: Immunologic evaluations performed on study patients will be compared with a matched group of 20

control patients receiving conventional immunosuppressive therapy and participating in an ongoing observational trial regarding immunologic mechanisms contributing to rejection in kidney transplant patients.

Criteria for Evaluation:

Primary Outcome Measures:

- Donor specific antibody testing at Month 6
- Cell surface cytokine secretion in response to donor cell antigen by direct and indirect stimulation at Month 6
- Cell surface cytokine secretion in response to CMV and EBV antigens by direct and indirect stimulation at Month 6
- Immunophenotyping to determine overall immune profile at Month 6
- Patient and functional graft survival in stable renal transplant recipients

Secondary Outcome Measures:

- Donor specific antibody testing at Months 1 and 3 (and month 12 if continuing in study)
- Cell surface cytokine secretion in response to donor cell antigen by direct and indirect stimulation at Months 1 and 3 (and month 12 if continuing in study)
- Cell surface cytokine secretion in response to CMV and EBV antigens by direct and indirect stimulation at Months 1 and 3 (and month 12 if continuing in study)

Statistical Methods: A sample size of 20 subjects will be enrolled. Because of the exploratory nature of this study is not possible to estimate power for this study size. Comparison between groups will be performed by Mann Whitney U test. In addition, a comparison will be made between patients' baseline and week 24 levels. ANOVA repeated measurement analysis will be used to evaluate immune measurements taken over time as compared with control patients.

10.5 Institutional Review Board (IRB)
10.6 Records Retention
11 GLOSSARY OF TERMS AND LIST OF ABBREVIATIONS
11.1 Glossary of Terms
11.2 List of Abbreviations
12 REFERENCES

#### **1 INTRODUCTION**

1.1 Research Hypothesis

**Primary Hypothesis:** 

Conversion from CNI-based therapy to belatacept will be safe and effective for prevention of rejection, with a significant impact on antibody and T cell-mediated immune response as compared with control patients as measured in peripheral blood at 6 months after belatacept conversion.

Outcomes to be tested:

- Belatacept-treated subjects will not have a greater incidence of SAEs as compared with control patients
- Belatacept-treated subjects will have similar rates of acute rejection as compared with control patients
- Belatacept-treated subjects will have a lower donor-specific antibody level at 6 months compared with control patients
- Belatacept-treated subjects will have a decrease in the frequency of alloantigen specific T cells over time as compared with control patients
- Belatacept-treated subjects will have a decrease in the frequency virus specific T cells over time as compared with control patients
- Belatacept-treated subjects will have a greater percentage of naïve and central memory T cells and a lower percentage of activated T cells as compared with control patients

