#### **2 STUDY OBJECTIVES**

#### 2.1 Primary Objectives

Primary Outcome Measures:

- Donor specific antibody testing at Month 6
- Cell surface cytokine secretion in response to donor cell antigen by direct and indirect stimulation at Month 6
- Cell surface cytokine secretion in response to CMV and EBV antigens by direct and indirect stimulation at Month 6
- Immunophenotyping to determine overall immune profile at Month 6
- Survival and rejection in patients switched to belatacept at 12 months post transplant as compared with patients treated with conventional therapy at our center.

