	Defined Cell Population	FITC	PE	PerCP	APC	Pac	PE-
						Blue	Cy7
1	Central/effector	CD57	CCR7	CD3	CD45RA	CD8	CD4
	memory, naïve T cells						
2	Activation, memory	CD45RA	CCR5	CD3	CD95	CD8	CD4
3	Activation, effectors	CD45RA	HLA-DR	CD3	CD38	CD8	CD4
4	NK cells	CD161	CD94	CD3	CD56	CD16	
5	B cells	CD19	CD27	CD20	CD38	CD3	
6	T regs	FoxP3	CD103	CD4	CD25	CD3	

In addition we will analyze rates of rejection and patient and graft survival at 6 and 12 months post transplant as compared with patients receiving conventional immunosuppression regimens at our center.

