#### Efficacy and safety

As an additional primary analysis, subject and graft survival at 6 months will be determined within each group. GFR measured at baseline and months 1, 3, 6, and 12 months will be descriptively summarized. Cumulative rates of acute and chronic rejection, and chronic allograft nephropathy, will be summarized, as well as incidence of post-transplant diabetes.

All AEs and SAEs since transplantation will be summarized for the patients receiving belatacept. For the control patients, rates of rejection, PTLD, and death will be summarized.

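### The SAE comparison with controls has no planned analysis, belatacept adverse events are counted from before the drug, and only belatacept subjects must be rejection-free when the rejection comparison starts

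*Combined protocol and SAP*

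**What the plan says.** **Hypotheses.** Section 1.1, under the outcomes to be tested, includes "Belatacept-treated subjects will not have a greater incidence of SAEs as compared with control patients" and "Belatacept-treated subjects will have similar rates of acute rejection as compared with control patients". The synopsis hypothesis adds "comparable safety and efficacy as compared with calcineurin inhibitor (CNI) based regimens".

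**Planned analysis.** Section 4.2 (Efficacy and safety) states: "All AEs and SAEs since transplantation will be summarized for the patients receiving belatacept". The next sentence is "For the control patients, rates of rejection, PTLD, and death will be summarized". It also says that "subject and graft survival at 6 months will be determined within each group", without saying what the 6 months are counted from.

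**Time origin for rejection and survival.** Section 2.1 lists as a primary outcome "Survival and rejection in patients switched to belatacept at 12 months post transplant as compared with patients treated with conventional therapy at our center". Section 3.1.3 says "we will analyze rates of rejection and patient and graft survival at 6 and 12 months post transplant", again against patients on conventional regimens at the centre.

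**Who is compared.** Belatacept subjects enter within 3 months of transplantation (7.2.1), and exclusion 9 in 5.2 removes anyone with biopsy-proven acute rejection in that period. Controls come from an observational study open to all kidney transplant recipients at the centre (4.1). They are matched on age, sex, donor type and DSA level (3.1.3), not on rejection history or time since transplantation.

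**AE collection.** Section 9.2 starts non-serious AE collection at the first study drug, or at an observational period that sets a baseline. Section 7.2.2 records pretreatment AEs on Day 1.

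**The concern.** Three defects affect the safety and efficacy conclusions. First, even a descriptive comparison of SAE incidence needs a figure from each group, and 4.2 plans one from belatacept patients only. The protocol does not say whether the observational study records SAEs in controls.

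Second, counting from transplantation puts events that happened on CNI, before any belatacept, into the belatacept safety summary. That start also does not fit the collection start in 9.2.

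Third, a belatacept subject cannot contribute a biopsy-proven rejection between transplantation and the switch, because such a patient would not have been enrolled. A control can. The two groups share a nominal origin but not the same time at risk, and the difference favours belatacept even if the drug does nothing.

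Two lesser points follow. Sections 2.1 and 3.1.3 do not say whether the comparator for rejection and survival is the 20 matched controls. The claims of similar and comparable results also have no margin or interval. Survival and rejection are among the primary outcomes in 2.1, so this is not peripheral.

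**Working it through.** The plan gives no power, margin or effect size for SAEs or rejection, so there is no figure of its own to reproduce. Points 1 and 2 compare text with text; the later sizes are illustrations.

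**1. SAE item.** 1.1 needs SAE incidence in both groups. 4.2 supplies it for belatacept and supplies rejection, PTLD, death and survival for controls. These overlap with SAEs but are not total SAE incidence. No other section fills the gap.

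**2. Events before the drug.** Let *m* be the months from transplantation to first infusion (0 to 3, from 7.2.1). Week 24 is 24 × 7 / 30.44 = 5.52 months after first infusion, and week 48 is 11.04. The share of the counted window before first infusion is m/(m + 5.52) or m/(m + 11.04):

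| m | to week 24 | to week 48 |
|---|---|---|
| 0 | 0% | 0% |
| 1 | 15.3% | 8.3% |
| 2 | 26.6% | 15.3% |
| 3 | 35.2% | 21.4% |

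This is calendar time, not a bias estimate. As an example with assumed rates, suppose 20% of subjects have an SAE after the switch. If 10% had one before it, incidence from transplantation is 1 − 0.90 × 0.80 = 28%; if 30% did, it is 1 − 0.70 × 0.80 = 44%.

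**3. Rejection-free entry.** Let *r* be the 12-month rejection rate from transplantation, and *f* the share of first-year rejections that fall before the switch. With no drug effect, controls have rate r. Belatacept subjects, being rejection-free at the switch, have rate (r − rf)/(1 − rf). Section 7.3.6 gives r = 0.10 (for cyclosporine); f is assumed. For example, f = 0.25 gives (0.10 − 0.025)/(1 − 0.025) = 7.69%.

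| f | meaning | belatacept rate | difference from 10% |
|---|---|---|---|
| 0 | switch near transplantation | 10.0% | 0 |
| 1/12 | month 1, even spread | 9.24% | 0.76 points |
| 2/12 | month 2, even spread | 8.47% | 1.53 |
| 3/12 | month 3, even spread | 7.69% | 2.31 |
| 0.50 | half precede the switch | 5.26% | 4.74 |
| 0.75 | three quarters precede it | 2.70% | 7.30 |

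In 20 patients this is 2.0 expected control rejections against 1.5, 1.1 and 0.5 for f = 0.25, 0.50 and 0.75. With r = 0.05 the difference is 1.2 points (f = 0.25) or 3.7 (f = 0.75); with r = 0.20 it is 4.2 or 14.1.

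**4. Unstated origin.** For a subject switched at month 3, 6 months post transplant is 6 − 3 = 3 months after the switch, while 6 months of belatacept ends at 3 + 6 = 9 months post transplant. Section 4.2 does not say which is meant.

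**5. Precision, 20 belatacept subjects, 10% observed rejection.**
- 2/20, Wilson 95% interval: 2.8% to 30.1%.
- 2/20 v 2/20, independent groups (Newcombe): −21.4 to +21.4 points.
- 20 matched pairs (Tango score): ±23.0 points with 2 and 2 discordant pairs; ±19.9 with 1 and 1.
- Against a very large centre group fixed at 10%: 2.8 − 10 = −7.2 to 30.1 − 10 = +20.1 points.

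None of these comparators supports a statement of similarity.

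**The case against.** The best case on the other side has five parts.

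- **SAEs are partly covered.** Controls do get death, PTLD and rejection; under 9.2 death is an SAE and cancer is handled as one. This stands as a limit on the gap: what is missing is the remaining control SAEs. It does not supply the total incidence that 1.1 compares.
- **Early events can be separated.** 9.2 requires onset and relationship for every AE, so events before infusion can be split off by date. True, and it makes the repair easy. But 4.2 as written does not split them.
- **Time alignment was considered.** 4.2 takes controls at a comparable time point, and 4.1 says their samples were stored at similar times after transplantation. Those statements concern the immune assays. They set neither an index date nor a rejection-free condition for clinical events.
- **The rejection effect may be small.** Under even spread it is at most 2.3 points, less than half a patient in 20 and far inside the ±21-point interval. The 10% figure is for cyclosporine and acute rejection generally, whereas exclusion 9 covers biopsy-proven rejection and subjects may be on tacrolimus. All of this is fair: the size is uncertain. The bias is nevertheless built into the design and can be removed by selection.
- **The study is exploratory, and patients at the centre most naturally means the matched controls.** Reasonable. The comparator and interval points are therefore clarifications and do not carry the concern.

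**Conclusion.** The concern holds and should be fixed. The SAE item in 1.1 has no matching analysis in 4.2, the belatacept AE summary includes events before the drug, and rejection before the switch can count only in controls.

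The rejection-free condition alone moves the 12-month comparison toward belatacept. With 10% first-year rejection and no drug effect, the shift is 0 to 2.3 points under even spread and 4.7 to 7.3 points if half to three quarters of rejections come early. That share is an assumption. The net direction over all unmatched entry criteria (for example PRA and zero-mismatch donors) is unknown. With intervals of about ±20 points, the planned summaries cannot establish similar rejection or comparable safety. The point does not bear on the immunologic endpoints.

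**What to change.** 1. **4.2, belatacept events.** Summarise AEs and SAEs from first infusion, flag those during the CNI taper, and list earlier events separately. State one collection start and make 9.2 agree with it.
2. **4.2, controls.** Give each control an index date at the same time after transplantation as the matched subject's first infusion. Use only controls who at that date are alive, have a functioning graft and have had no biopsy-proven rejection. Count comparative events in both groups from it. Where records allow, apply the other immunologic exclusions of 5.2 to controls too.
3. **1.1, SAE item.** If the observational study records SAEs, summarise them in controls from the index date. Otherwise restate the item as a descriptive summary for belatacept only.
4. **Synopsis, 1.1, 2.1, 3.1.3 and 4.2.** Name the matched controls as the comparator for rejection and survival, state the origin of the 6 and 12 months, and replace the similarity wording with: *Differences in rejection, PTLD, death and graft loss will be reported with 95% confidence intervals; no claim of similarity will be made.* Say whether the intervals are for matched pairs or independent groups.

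**Cost.** Wording changes plus an added control-selection step; no extra subjects or visits. The pool of eligible controls shrinks by an amount the documents do not let us estimate, and the same controls serve the immunologic endpoints. The safety and efficacy conclusion becomes more modest. Counts from first infusion still include CNI exposure during the taper (6.2.1), so they are not CNI-free.

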#### 3.1.2 Overview

This is an open label, single center clinical trial. All subjects will have undergone kidney transplantation with induction immunosuppression and will be on maintenance therapy with a CNI (tacrolimus or cyclosporine) plus mycophenolate mofetil and corticosteroid maintenance therapy at the time of enrollment. 20 subjects with evidence of CNI toxicity (see definition below) in the first three months after transplant will be enrolled to switch to the belatacept regimen. These enrolled subjects will be compared with 20 matched patients from an ongoing observational study of kidney transplant patients at our center.

All subjects will also receive induction with basiliximab and a background maintenance immunosuppressive regimen of MMF and corticosteroids.

Study patients will receive intravenous belatacept at 5mg/kg every two weeks at day 1 and weeks 2, 4, 6, and 8, and then monthly at months 3, 4, and 5. At month 6 patients may elect to continue for an additional six-month period of belatacept administration

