#### 3.4 Sample Size Determination

Because of the exploratory nature of this analysis, it is not possible to estimate power for this study, a goal of 20 patients was used similar to other immunologic pilot studies and is a reasonable goal for rapid accrual at our center.

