7.3.6 Potential for premature termination of clinical trial

The incidence of acute rejection during the first year post-transplant is typically about 10% for a cyclosporine based immunosuppression regimen [4]. If a two-fold or greater (>=20%) incidence of acute rejection is observed, the patient demographics and data collected will be reviewed and the trial will be considered for premature termination. Because of the small

number of patients participating in this trial, an up to two-fold deviation from expected rates was established.

8 Drug Product

8.1 Study Product Bristol-Myers Squibb will supply Belatacept.:

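### Similar acute rejection is listed as an outcome to be tested, but 20 versus 20 matched patients with no margin and no planned interval cannot support a conclusion of similarity

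*Combined protocol and SAP*

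**What the plan says.** Section 1.1 puts clinical claims under its primary hypothesis. Under "Outcomes to be tested" it includes: "Belatacept-treated subjects will have similar rates of acute rejection as compared with control patients". The research hypothesis in the synopsis adds "comparable safety and efficacy as compared with calcineurin inhibitor (CNI) based regimens". Section 1.4 acknowledges a potential risk of more acute rejection on belatacept.

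On numbers, the synopsis says "A sample size of 20 subjects will be enrolled", and section 3.1.2 says "These enrolled subjects will be compared with 20 matched patients from an ongoing observational study of kidney transplant patients at our center". Section 3.4 states: "Because of the exploratory nature of this analysis, it is not possible to estimate power for this study".

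On analysis, section 4.2 (Efficacy and safety) says: "Cumulative rates of acute and chronic rejection, and chronic allograft nephropathy, will be summarized". The Mann-Whitney test in section 4.2 is assigned to the immune measures. No margin, significance level, test or interval is given for rejection anywhere.

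Section 7.3.6 takes about 10% as the usual first-year acute rejection rate on a cyclosporine regimen. It provides for review and possible early termination as follows: "If a two-fold or greater (>=20%) incidence of acute rejection is observed".

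**The concern.** A claim of similar rates needs either a margin with an interval that lies inside it, or at least an interval that shows which differences remain possible. This plan has neither. The only route left to the claim is to set two small counts side by side and see no striking gap. In groups of 20 that says little, because the data would also fit a clinically important excess of rejection.

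At stake is how the result may be worded. Section 1.4 names more rejection as a possible harm, and bare rates set against a hypothesis of similarity make it easy to read absence of evidence as reassurance.

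**Working it through.** The plan states no power, margin or effect size for rejection, so there is no figure to reproduce. The check asks what 20 versus 20 can show.

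**Inputs from the documents**
- Belatacept n = 20 (synopsis) and matched controls n = 20 (section 3.1.2).
- Reference rejection rate 10%, with 20% or more as the review level (section 7.3.6). Expected count at 10%: 0.10 × 20 = 2. Review level: 0.20 × 20 = 4.

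**Assumptions of mine**
- Independent groups, and 95% two-sided intervals.
- For the power figures only, a two-sided Fisher test at 0.05. The plan names no such test.

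**1. Interval for the difference (Newcombe, from Wilson limits)**

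Wilson limits for x/n, with p = x/n: [p + z²/(2n) ± z√(p(1−p)/n + z²/(4n²))] / (1 + z²/n), with z = 1.96 and z² = 3.8415.

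For 2/20:
- centre = (0.10 + 0.0960)/1.1921 = 0.1645
- half-width = 1.96 × √(0.0045 + 0.0024)/1.1921 = 0.1366
- limits = 0.028 to 0.301

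Newcombe limits for 2/20 v 2/20: 0 ± √[(0.100 − 0.028)² + (0.301 − 0.100)²] = ±0.214.

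For 0/20 the Wilson limits are 0 to 0.161, so 0/20 v 0/20 gives ±0.161.

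| Belatacept v control | Difference (points) | 95% interval (points) |
|---|---|---|
| 0/20 v 0/20 | 0 | -16.1 to +16.1 |
| 2/20 v 2/20 | 0 | -21.4 to +21.4 |
| 4/20 v 2/20 | +10 | -13.4 to +32.8 |

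A doubling from 10% to 20% is a difference of +10 points. It lies inside every interval, including those with equal counts.

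**2. What a significance test would do, if one were used**

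Power = Σ P(x) P(y) over all pairs with belatacept higher and Fisher p ≤ 0.05, where x ~ Bin(20, belatacept rate) and y ~ Bin(20, 0.10).

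| True rates | Power |
|---|---|
| 20% v 10% | 7% |
| 30% v 10% | 24% |
| 40% v 10% | 49% |
| 50% v 10% | 74% |

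With 2/20 control rejections, belatacept would need 9/20 to reach p ≤ 0.05. If the true rates were 20% v 10%, belatacept would still show an equal or lower count in 25% of trials.

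**3. The review trigger in section 7.3.6**

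I read it as 4 or more of the 20 belatacept patients, assessed once with all 20 followed. P(fires) = 1 − P(X ≤ 3), X ~ Bin(20, p).
- True 10%: 1 − 0.867 = 13%
- True 20%: 1 − 0.411 = 59%
- True 30%: 1 − 0.107 = 89%

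**4. What a similarity claim would need**

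For 10% in both groups, a 10-point margin, one-sided 0.025 and 80% power: n = 2 × 0.10 × 0.90 × (1.960 + 0.842)² / 0.10² ≈ 141.3, so 142 per group. I give this to show the gap, not as a proposal.

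**5. Comparability of the groups**

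Section 5.2 excludes study subjects with biopsy-proven rejection in the first three months after transplant. Section 3.1.3 matches on age, sex, donor type and DSA level, not on absence of earlier rejection. Sections 2.1 and 3.1.3 count rejection from transplant. Unless controls are restricted likewise, they can contribute early events that the belatacept group cannot have, which would favour belatacept. No confidence interval covers that.

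**The case against.** The strongest reply is that the plan already admits its limits. The synopsis and section 3.4 call the study exploratory and disclaim power, section 3.1.3 gives the purpose as immunologic mechanism, and section 4.2 promises only summaries of rejection. This stands. It makes the problem a mismatch between hypothesis and analysis, not a miscalculation, and it lowers the severity.

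A reader might infer that the trial would declare its clinical hypothesis met almost whatever the true rejection rate is. The documents do not support that. They contain no rule for declaring it met, and the Fisher test above is not planned. Even with that test, power would be 49% at 40% and 74% at 50%.

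A reader might also infer that a doubling would usually pass unnoticed. That holds for the two-group comparison only. The separate trigger in section 7.3.6 would flag a true 20% in 59% of trials and a true 30% in 89%. It is a review rule against a fixed 10%, however, so its not firing is not evidence of similarity.

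Nor is rejection plainly a primary endpoint. Sections 1.1 and 2.1 treat it so, but the primary lists in the synopsis and section 3.3, and the additional primary analysis in section 4.2, name survival.

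Finally, the comparator may not be the 20 matched controls: sections 2.1 and 3.1.3 refer to conventionally treated patients at the center, with no number. If there were 100 or 200 of them (assumed), Fisher power for 20% v 10% would be 23% or 26%, so the conclusion survives.

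**Conclusion.** The point holds as a mismatch between claim and plan. Similar acute rejection is listed for testing without a margin or an interval, and 20 versus 20 cannot support it: at the expected 10% per group the 95% interval is about ±21 points, and even with no events it is ±16.

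The interval widths are the main evidence and rest on 20 controls analysed as an independent group. The documents give no within-pair correlation, so any gain from matching cannot be sized. The power figures depend on an assumed two-sided 0.05 Fisher test. The 10% is a first-year cyclosporine rate. Excluding early rejectors may lower it; at 5% doubling to 10%, Fisher power falls to 2%.

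This is worth correcting before results are written, but it does not invalidate the study or call for a larger one.

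**What to change.** - **Synopsis and section 1.1:** replace the similarity and comparability wording for rejection with the aim of estimating the difference in acute rejection between groups.
- **Section 4.2, analysis:** report each group's rate and the difference with a two-sided 95% interval (Newcombe, for example). State that equal counts or a non-significant difference will not be reported as similarity.
- **Section 4.2, comparator:** name it, and reconcile section 3.1.2 (20 matched controls) with sections 2.1 and 3.1.3 (patients at the center). For this comparison, restrict controls to those free of rejection at the matched time point, and note that the interval covers sampling error only.
- **Section 3.4:** state the expected precision, about ±21 points at 10% per group with 20 controls. Recalculate it if another comparator is chosen.

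The cost is wording in four places, one interval calculation and a check of control records for earlier rejection, which may shrink the pool of eligible controls. No patients, visits or assays are added. The downside for the investigators is a less favourable clinical claim.
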